9.3 Efficacy Assessments

Various outcome assessments will explore the impact of each dose of RD-X19 treatment compared to sham on the sustained resolution of clinical signs and symptoms (in all subjects, and separately in all mild subjects), COVID-19 clinical outcomes, and the \log_{10} reduction of SARS-CoV-2 viral load.

The primary efficacy outcomes are:

- Sustained resolution of COVID-19 signs and symptoms in all subjects (with Mild or Moderate disease at baseline)
- Sustained resolution of COVID-19 signs and symptoms in subjects with Mild disease at baseline

Subjects will be instructed to fill out a diary card or electronic equivalent to assess their signs and symptoms of disease twice daily. Each of the eight symptoms will be rated on a scale from none (0) to severe (3).

Success on sustained resolution will be recorded as at the time (in hours) when cough, sore throat, nasal congestion, headache, chills and or sweats, myalgia, fatigue, and nausea (with or without

vomiting) have been assessed by the subject as none (0) or mild (1) and all symptoms remain at or below 1 until study Day 14.

*Subjects reporting a persistent fever via oral temperature of 100.5 (36 hours or more) or SpO₂ levels <96% with shortness of breath fail to meet the success criterion on that day even if all other symptoms are reported as none (0) or mild (1).

Additional secondary efficacy outcomes include:

- Proportion of study subjects who achieve Day 8 Composite Resolution defined as both a negative SARS-CoV-2 antigen test within the window for Visit 4 (Days 7 – 9) and all symptoms assessed by the subject as none (0) or mild (1), absence of fever and SpO₂ ≥96% without shortness of breath at study day 8 (as reported on the Diary Card Day 8-Assessment 1).
- Proportion of study subjects who experience worsening of COVID-19 disease as defined by an increase of the composite COVID-19 severity score greater than baseline at any point in the study on or after day 3.
- Proportion of study subjects who affirm they have returned to Pre-COVID Health at day 8 and day 14.
- Proportion of study subjects progressing to “severe” clinical outcomes associated with COVID-19.
- Mean change in nasopharyngeal SARS-CoV-2 viral load from baseline on days 3, 5, 8, and 14 by RT-qPCR
- Proportion of subjects demonstrating clearance of viral infection, defined as a negative nasopharyngeal swab via RT-qPCR on each of Days 3, 5, 8 and 14.

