  - b) In the past 24 hours, have you returned to your usual activities (before your COVID-19 illness)?
- Proportion of study subjects with any one or more of the following severe clinical outcomes (including proportions of study subjects for each individual outcome):

- 1) who require medical attention or intervention attributed to COVID-19
- 2) who progress to severe systemic illness with respiratory rate  $\geq 30$ /minute, heart rate  $\geq 125$ , O2 saturation  $\leq 93\%$  on room air or PaO2/FiO2  $\leq 300$  mm Hg, or lung infiltrates upon imaging  $>50\%$ .
- 3) who require hospitalization for severe COVID-19
- 4) who require endotracheal ventilation or ECMO with or without the use of solumedrol
- 5) who die

Secondary virologic endpoints:

- Mean change in nasopharyngeal viral load on days 3, 5, 8, and 14
- Geometric mean nasopharyngeal viral load at baseline and on days 3, 5, 8, and 14
- Proportion of subjects demonstrating clearance of viral infection, defined as a negative nasopharyngeal swab via RT-qPCR as assessed on Days 3, 5, 8 and 14

Exploratory assessments of effects of RD-X19 in saliva viral load include:

- Mean change in saliva viral load on days 3, 5, 8, and 14
- Geometric mean saliva viral load at baseline and on days 3, 5, 8, and 14

Exploratory assessment of effects of RD-X19 in oral microbiome includes:

- Change in  $\alpha$  and  $\beta$  diversity in microbial flora from baseline on day 8 and day 14 as analyzed by 16S rRNA subunit analysis from frozen saliva samples

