## 5.1 Methodological Considerations

### General Conventions

SAS software (version 9.4 or higher) will be used for all data analyses and tabulations.

Data for all investigational centers will be pooled for analysis. The sham groups from different cohorts will not be combined for the analyses unless otherwise specified. For all analyses, subjects will be analyzed based on actual treatment received.

Unless specified elsewhere, baseline is defined as the last available measurement prior to administration of study treatment. Change from baseline will be calculated as the post-baseline value minus the baseline value.

Summary tables will include the data based upon the protocol scheduled time points. For subjects who are early discontinued from the study or have visits outside of the allowed window, all efficacy assessments captured at the visit will be assigned to the protocol scheduled time point as follows:

Visit of Treatment Period	Range for ET / Visit Re-allocation*
Visit 2 / Day 3	Study Day 1 to 3
Visit 3 / Day 5 ( $\pm$ 1 day)	Study Day 4 to 6
Visit 4 / Day 8 ( $\pm$ 1 day)	Study Day 7 to 9
Visit 5 / Day 14 ( $\pm$ 2 day)	Study Day $\geq$ 10

\*Study day = date of visit - date of first treatment + 1

Descriptive statistics of continuous variables will include n, mean, standard deviation (SD), median, and range. Generally, the minimum and maximum values will be presented to the same decimal precision as the raw values, the mean and median values to one additional decimal, and the SD, to two more decimal places than the raw values. Summaries for categorical data will include frequencies and percentages. Percentages will be presented to one decimal place.

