**PROC LIFETEST DATA=**data**in PLOTS=SURVIVAL(FAILURE);**  
    **WHERE trt in (1,3);**  
    **TIME hours\*cnsr(1);**  
    **STRATA trt;**  
**RUN;**

### 5.5.2 Analysis of Secondary and Exploratory Endpoints

All secondary clinical, virologic, and exploratory efficacy endpoints will be summarized using descriptive statistics by visit (as appropriate) for each treatment group.

For virologic outcome assessments, subjects without a Baseline biospecimen collected and/or the Baseline biospecimen determined to NOT be an analysis-qualified sample, will be excluded from these analyses.

Analysis-qualified samples are defined as nasopharyngeal and saliva SARS-CoV-2 biospecimen samples that have no sample Violations as outlined in the Biospecimen Violation and Biospecimen Deviation (BVBD) Log. Any samples that are not analysis-qualified, designated by “Valid biospecimen = N” will be replaced by missing values (prior to the multiple imputation described below).

Viral load (log base 10 copies/mL) and cycle threshold (Ct) data are continuous in nature but may be reported as “undetermined” or “inconclusive” or “<LOQ”.

For analysis-qualified samples, results of “undetermined” and “<LOQ” for N1 copies/mL will be handled as follows for data summary purpose:

- For viral load reported as “Undetermined”, value 1 will be used to calculate descriptive statistics. This will support the need for logarithm transformation.
- For viral load reported as “<LOQ”, value  $5 \times 10^1$  will be used to calculate descriptive statistics.

Sample values reported as either “Inconclusive” N1 Ct viral load or with an “Undetermined” RNase P (RP) internal control Ct value will be replaced by missing values prior to the multiple imputation (MI) described below.

MI will be performed separately for saliva samples and nasopharyngeal samples and for each treatment via a two-step process for subjects with non-missing baseline. Viral load values will be log10-transformed before MI. Missing data occurring for an intermediate visit will be imputed first using a Markov Chain Monte Carlo (MCMC) method. As a result, a monotone missingness pattern will be obtained for the data to be fully imputed. The subsequent imputation will use Monotone Regression to produce 100 imputed datasets where the remaining missing data are filled in.

The SAS code for MI is as follows:

- Saliva samples: random number = 184962 as the seed for the first Step and 64849 as the seed for the second step.

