Table 14.2.3.1.1 – Summary of Secondary Virologic Outcomes: Log10-Transformed Nasopharyngeal Viral Load by Visit for Subjects with Mild and Moderate Disease at Baseline, Full Analysis Set

Study Visit	Statistics	RD-X19 from Final Cohort	RD-X19 from Cohort A	Pooled RD-X19	Pooled Sham
Visit 1 / Day 1	N	XX	XX	XX	XX
	Mean ± SD	XX.X ± XX.X	XX.X ± XX.X	XX.X ± XX.X	XX.X ± XX.X
	Median	XX.X	XX.X	XX.X	XX.X
	Min, Max	XX, XX	XX, XX	XX, XX	XX, XX
	Geometric Mean on Original Scale	XX.X	XX.X	XX.X	XX.X
Visit 2 / Day 3	N	XX	XX	XX	XX
	Mean ± SD	XX.X ± XX.X	XX.X ± XX.X	XX.X ± XX.X	XX.X ± XX.X
	Median	XX.X	XX.X	XX.X	XX.X
	Min, Max	XX, XX	XX, XX	XX, XX	XX, XX
	Geometric Mean on Original Scale	XX.X	XX.X	XX.X	XX.X
Visit 3 / Day 5					
Visit 4 / Day 8					
Visit 5 / Day 14					

To deal with missing data multiple imputation (MI) has been carried out on the Log10 scale. The mean of the 100 MI copies is used in each case to replace the missing value. Summary statistics are calculated after this imputation for missing data.

Note: Geometric Means are computed by exponentiating (base 10) the Means of the log10-transformed viral load.

Source: Listing 16.x.x

O:\Studies\EmitBio\EB-P20-01\Biometrics\Programs\Tables\xxx.sas ran on Month Day, Year at hh:mm on data from Month Day, Year.

Repeat Table 14.2.3.1.1 for the following:

Table 14.2.3.1.2 – Summary of Secondary Virologic Outcomes: Log10-Transformed Nasopharyngeal Viral Load by Visit for Subjects with Mild Disease at Baseline, Full Analysis Set

Repeat Tables 14.2.3.1.1 and 14.2.3.1.2 for the following:

Table 14.2.3.2.1 – Summary of Secondary Virologic Outcomes: Log10-Transformed nasopharyngeal Viral Load by Visit for Subjects with Mild and Moderate Disease at Baseline, Modified Full Analysis Set

Table 14.2.3.2.2 – Summary of Secondary Virologic Outcomes: Log10-Transformed nasopharyngeal Viral Load by Visit for Subjects with Mild Disease at Baseline, Modified Full Analysis Set

Table 14.2.3.3.1 – Summary of Secondary Virologic Outcomes: Log10-Transformed Nasopharyngeal Viral Load by Visit for Subjects with Mild and Moderate Disease at Baseline, Per-Protocol Population

Table 14.2.3.3.2 – Summary of Secondary Virologic Outcomes: Log10-Transformed Nasopharyngeal Viral Load by Visit for Subjects with Mild Disease at Baseline, Per-Protocol Population

Table 14.2.4.1 – Summary of Secondary Virologic Outcomes: Proportion of Subjects with Clearance of Viral Infection by Visit for Subjects with Mild and Moderate Disease at Baseline

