Study Visit	Statistics	RD-X19 from Final Cohort	RD-X19 from Cohort A	Pooled RD-X19	Pooled Sham
Visit 1 / Day 1	N	XX	XX	XX	XX
	Mean $\pm$ SD	XX.X $\pm$ XX.X	XX.X $\pm$ XX.X	XX.X $\pm$ XX.X	XX.X $\pm$ XX.X
	Median	XX.X	XX.X	XX.X	XX.X
	Min, Max	XX, XX	XX, XX	XX, XX	XX, XX
	Geometric Mean on Original Scale	XX.X	XX.X	XX.X	XX.X
Visit 2 / Day 3	N	XX	XX	XX	XX
	Mean $\pm$ SD	XX.X $\pm$ XX.X	XX.X $\pm$ XX.X	XX.X $\pm$ XX.X	XX.X $\pm$ XX.X
	Median	XX.X	XX.X	XX.X	XX.X
	Min, Max	XX, XX	XX, XX	XX, XX	XX, XX
	Geometric Mean on Original Scale	XX.X	XX.X	XX.X	XX.X
Visit 3 / Day 5					
Visit 4 / Day 8					
Visit 5 / Day 14					

To deal with missing data multiple imputation (MI) has been carried out on the Log10 scale. The mean of the 100 MI copies is used in each case to replace the missing value. Summary statistics are calculated after this imputation for missing data.

Note: Geometric Means are computed by exponentiating (base 10) the Means of the log10-transformed viral load.

Source: Listing 16.x.x

O:\Studies\EmitBio\EB-P20-01\Biometrics\Programs\Tables\xxx.sas ran on Month Day, Year at hh:mm on data from Month Day, Year.

Repeat Table 14.2.5.1 for the following:

Table 14.2.5.2 – Summary of Exploratory Virologic Outcomes: Log10-Transformed Saliva Viral Load by Visit for Modified Full Analysis Set

Table 14.2.5.3 – Summary of Secondary Virologic Outcomes: Log10-Transformed Saliva Viral Load by Visit for Per-Protocol Population

Table 14.3.1.1 - Treatment-Emergent Adverse Events by System Organ Class and Preferred Term for Safety Population

System Organ Class Preferred Term	RD-X19 from Final Cohort (N=XX) n (%)	RD-X19 from Cohort A (N=XX) n (%)	Pooled RD-X19 (N=XX) n (%)	Pooled Sham (N=XX) n (%)
Subjects Reporting at Least One Adverse Event	XX (XX.X)	XX (XX.X)	XX (XX.X)	XX (XX.X)
System Organ Class #1	XX (XX.X)	XX (XX.X)	XX (XX.X)	XX (XX.X)
Preferred Term #1	XX (XX.X)	XX (XX.X)	XX (XX.X)	XX (XX.X)
Preferred Term #2	XX (XX.X)	XX (XX.X)	XX (XX.X)	XX (XX.X)
...				
System Organ Class #2	XX (XX.X)	XX (XX.X)	XX (XX.X)	XX (XX.X)
Preferred Term #1	XX (XX.X)	XX (XX.X)	XX (XX.X)	XX (XX.X)
Preferred Term #2	XX (XX.X)	XX (XX.X)	XX (XX.X)	XX (XX.X)
...				

Counts reflect numbers of subjects reporting one or more TEAE that map to the MedDRA system organ class/preferred term. At each level of summarization (system organ class or preferred term), subjects reporting more than one TEAE are counted only once.

Source: Listing 16.x.x

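### The viral load tables omit change from baseline and the Final Cohort sham column, so the spread of a listed endpoint and the precision of the randomised contrast cannot be recovered from them

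*SAP*

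**What the plan says.** Protocol 9.3 lists "Mean change in nasopharyngeal SARS-CoV-2 viral load from baseline on days 3, 5, 8, and 14 by RT-qPCR" among the secondary outcomes, and Protocol 4.1.2 and 6.4 agree. SAP 3.2 has "Mean change in nasopharyngeal viral load on days 3, 5, 8, and 14" as its own bullet, separate from the geometric mean by visit. The same two measures in saliva are exploratory.

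The SAP text covers the endpoint. Under General Conventions (5.1), "Change from baseline will be calculated as the post-baseline value minus the baseline value", and "Descriptive statistics of continuous variables will include n, mean, standard deviation (SD), median, and range". Section 5.5.2 then states: "All secondary clinical, virologic, and exploratory efficacy endpoints will be summarized using descriptive statistics by visit (as appropriate) for each treatment group".

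The shells do not follow through. The one titled "Summary of Secondary Virologic Outcomes: Log10-Transformed Nasopharyngeal Viral Load by Visit for Subjects with Mild and Moderate Disease at Baseline, Full Analysis Set" (Table 14.2.3.1.1) prints N, mean ± SD, median, minimum and maximum, and "Geometric Mean on Original Scale", all of the value at the visit. The five other nasopharyngeal tables (14.2.3.x) and the three saliva tables (14.2.5.x) repeat this layout. The columns are Final Cohort RD-X19, Cohort A RD-X19, Pooled RD-X19 and Pooled Sham. By contrast, the vital-sign and methemoglobin shells (14.3.4.x, 14.3.5) have change-from-baseline rows.

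**The concern.** Two safety measurements get change-from-baseline rows, while an efficacy endpoint defined as a change does not. A programmer who builds the tables from the shells would deliver visit means only.

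The columns add a second gap. SAP section 5 permits pooled sham for secondary tabulations, but the two cohorts recruit differently. Each cohort first targets 30 seronegative subjects, whereas the optional expansion of the Final Cohort takes all serostatuses. Final Cohort RD-X19 against Pooled Sham is therefore not a comparison within one randomisation, and these tables have no Final Cohort Sham column.

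Viral load reduction is the device's proposed mechanism and a headline result of the proof-of-concept study (Protocol 4.1), so readers will look for this comparison. From the tables as laid out, they could not judge how precise it is.

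**Working it through.** **No figure to reproduce.** Neither document gives an effect size, SD or power for viral load. The power statements concern the first primary endpoint.

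**Step 1: what can be recovered.** SAP 5.5.2 excludes subjects without a qualified baseline specimen and imputes later missing values, so N is the same at every visit. Then mean(Y − X) = mean(Y) − mean(X), where X is baseline and Y the visit value. In a simulated arm of 120, both sides equalled −3.1957. Mean change, and a crude difference from Pooled Sham, therefore follow from the printed means.

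**Step 2: what cannot.** SD(change) = √(s0² + s1² − 2·r·s0·s1), where s0 and s1 are the baseline and visit SDs and r their correlation. The shells give s0 and s1 but not r. Re-pairing the same simulated values left every visit mean and SD unchanged but moved the SD of change from 2.10 to 2.34. The median and range of change are lost in the same way.

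As an illustration, assume s0 = s1 = 2.0 log10, 120 RD-X19 subjects (two thirds of 180) and 70 pooled sham (60 + 10). The 95% half-width is 1.96 × SD × √(1/120 + 1/70), using SD(change) for the change score and s1·√(1 − r²) for the baseline-adjusted difference.

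| Assumed r | SD of change | Half-width, change | Half-width, baseline-adjusted |
|---|---|---|---|
| 0 | 2.83 | 0.83 | 0.59 |
| 0.2 | 2.53 | 0.75 | 0.58 |
| 0.4 | 2.19 | 0.65 | 0.54 |
| 0.6 | 1.79 | 0.53 | 0.47 |
| 0.8 | 1.26 | 0.37 | 0.35 |

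The same printed visit means and SDs fit every row.

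**Step 3: gain from baseline adjustment.** Take the standard error (SE) for comparing visit means as 1. With equal variances the change score has relative SE √(2 − 2r), and ANCOVA on baseline has √(1 − r²).

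| Assumed r | Change score | ANCOVA |
|---|---|---|
| 0.3 | √1.4 = 1.18 | √0.91 = 0.95 |
| 0.5 | √1.0 = 1.00 | √0.75 = 0.87 |
| 0.7 | √0.6 = 0.77 | √0.51 = 0.71 |

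ANCOVA's SE is 5% to 29% smaller than for visit means. Relative to the change score it is √((1 + r)/2) = 0.81, 0.87 and 0.92, that is, 19% to 8% smaller.

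**Step 4: chance imbalance at baseline.** The SAP's multiplicity example has 98 + 76 = 174 subjects. At 2:1 that is 116 and 58 (my assumption). The baseline difference between arms then has SD √(1/116 + 1/58) = 0.16 patient SDs.

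**Step 5: imputation.** SAP 5.5.2 and the table footnotes replace each missing value by the mean of its 100 imputed copies on the log10 scale before summarising. A model fitted to that single completed dataset treats imputed values as observed, and its interval is too narrow. The SD is understated for the same reason. Rubin's rules use total variance W + (1 + 1/100)·B, where W is the average within-imputation variance and B the variance of the estimate between imputations.

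**The case against.** A reader might infer that the endpoint is never produced. The documents do not support that. SAP 3.2, 5.1 and 5.5.2 together already call for n, mean, SD, median and range of every continuous secondary endpoint. SAP section 6 presents the shells as examples open to change, and mean change follows by subtraction in any case. This objection stands, and it reduces the missing rows to an inconsistency between text and shell.

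A reader might also take the lack of a formal comparison with sham for an oversight. It is a stated choice: Protocol 10.1 confines hypothesis testing to the two primary endpoints, and Protocol 10.4.1 and SAP 5.5.2 keep secondary endpoints descriptive. No document promises an adjusted difference or an interval for viral load. That stands too, so the adjusted estimate is offered as an improvement and carries no p-value.

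Nor is baseline imbalance hidden. Day 1 values appear in the same shells, and Table 14.1.3 shows baseline nasopharyngeal load. However, displaying an imbalance does not adjust for it.

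Finally, the precision figures are generic. Equal variances are doubtful when undetermined results are set to 1 copy (log10 = 0) and results below the limit of quantification to 50 copies, since values may gather at the floor by Day 14. This is fair, and the figures should be read as illustration only.

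**Conclusion.** The point holds in a limited form. A listed endpoint, whose mean and SD the SAP text implies, has no rows in any of the nine viral load shells. The shells also lack the sham column needed for the randomised Final Cohort contrast. Mean change can be derived from them; its SD, median and range, and the precision of that contrast, cannot.

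The change rows are a consistency correction. The baseline-adjusted difference is an inexpensive gain from a measurement already scheduled for every subject, usable in those with a qualified baseline specimen. The 5% to 29% reduction in standard error over comparing visit means rests on an assumed correlation of 0.3 to 0.7 and equal variances. The 0.16 figure rests on the SAP's example total of 174 split 2:1. No number in the documents changes, and the primary analysis is unaffected.

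**What to change.** Before unblinding:

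1. In Tables 14.2.3.x and 14.2.5.x, add change-from-baseline rows (n, mean, SD, median, range, log10 scale) for each post-baseline visit, laid out as in Table 14.3.4.1.
2. Add a Final Cohort Sham column to those tables.
3. For the Final Cohort, add a descriptive RD-X19 minus Sham difference at each post-baseline visit. Take it from ANCOVA with baseline log10 viral load as covariate, in subjects with a qualified baseline specimen, with a 95% CI and no p-value. Fit the model in each of the 100 imputed datasets and combine by Rubin's rules, not on data where each missing value has been replaced by the mean of its copies.

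The cost is extra rows and one column in nine tables, plus one standard model with a pooling step. It needs no new data and spends no alpha. The same rows added after unblinding would be post hoc.

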### 3.3 Sample Size Determination

The target number of subjects to be randomized per cohort is 30 individuals seronegative for SARS-CoV-2 Spike IgG antibodies (20 subjects to the RD-X19 treatment arm and 10 subjects for Sham control), for a minimum total of 60 subjects. At the sponsors option, the total number of subjects can be increased by an additional 150 total subjects to include all serostatuses after a dose has been selected based on adequate safety/tolerability observed for the final dose cohort.

Based on findings in the EB-P12-01, the hazard ratio observed for the time to sustained symptom resolution in that early feasibility trial was HR=0.4 between active RD-X19 and Sham.

The increased sample size in the Final Cohort (up to 180 total), with an anticipated roughly equal number of antibody positive to negative individuals enrolled during the option, will lead to approximately 90 seropositive and 90 seronegative subjects. The modified Full Analysis Set (mFAS) population containing only antibody negative subjects (as defined in Section 4, 60 RD-X19: 30 Sham) has at least 90% power to detect meaningful changes in SARS-CoV-2 symptom resolution from baseline (Hazard ratio of 0.4) for the first primary endpoint. These power calculations assume that testing will be carried out using  $\alpha = 0.025$  one-sided, up to a 20% dropout rate due to discontinuations or hospitalizations, as well as an assumption that the proportions of subjects having the event (for the first primary endpoint) by Day 14 is 85% for the RD-X19 arm and 75% for the Sham arm.

In the Full Analysis Set (FAS) for the Final Cohort, the primary analysis population including all randomized subjects receiving at least one treatment, the increased sample size (increase by a minimum of 100 RD-X19: 50 Sham) has at least 90% power to detect a Hazard ratio of 0.5 between RD-X19 and Sham for the first primary endpoint. These power calculations assume that testing will be carried out using  $\alpha = 0.025$  one-sided, as well as an assumption that the proportions of subjects having the event (for the first primary endpoint) by Day 14 is 90% for the RD-X19 arm and 85% for the Sham arm, with adjustment for multiple endpoints as described in Section 5.1.1.

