- Nasopharyngeal samples: random number = 133274 as the seed for the first Step and 485044 as the seed for the second step.

Where notation of main variables:

- Log\_dayX: log10-transformed viral load at Day X visit, where X=1, 3, 5, 8 and 14.

\*Step 1: MCMC fills interim missingness to make monotone;

```
PROC MI data=datain out=step1 seed=XXXXXX n impute=100;
  mcmc impute=monotone;
  var log_day1 log_day3 log_day5 log_day8 log_day14;
run;
```

\*Step 2: MI regression;

```
PROC MI data=step1 out=step2 seed=XXXXXX n impute=1
  var log_day1 log_day3 log_day5 log_day8 log_day14;
  monotone reg(log_day3 = log_day1); *for D3;
  monotone reg(log_day5 = log_day1 log_day3); *for D5;
  monotone reg(log_day8 = log_day1 log_day3 log_day5); *for D8;
  monotone reg(log_day14 = log_day1 log_day3 log_day5 log_day8);
  by _imputation_;
run;
```

If either of the above multiple imputation procedures fails to converge, then multiple imputation (for both calls to PROC MI) will only be carried out for the Final Cohort, in which case only one of the 3 dummy variables for treatment will be needed in the first call to PROC MI.

The imputed values will be converted back to original scale by raising 10 to the power. For each missing value, its geometric mean of the 100 MI copies will be derived prior to the calculation of the summary statistics.

For log10-transformed viral load data, geometric means will be computed by exponentiating (base 10) the group means of the log10-transformed viral load.

In conjuncture with above handling of the viral data scenarios, for purposes of this protocol, clearance of viral infection post baseline visit is defined as achievement of: [1] RP Ct  $\geq 0$ , AND [2] Average N1 Ct = “Undetermined”.

Subjects with missing nasopharyngeal samples at any post baseline visit will not be imputed for the purposes of determining the proportion of subjects demonstrating clearance of viral infection. Such cases will be determined to be a ‘failure’ at this visit/assessment as having not achieved the endpoint of clearance of viral infection. If a subject’s nasopharyngeal SARS-CoV-2 biospecimen sample at Visit X had a Violation as outlined in the Biospecimen Violation and Biospecimen Deviation Log, the subject will also be considered ‘FAILURE’ at Visit X.

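### The viral-load imputation omits baseline antibody and disease status, the factors that define the seronegative and mild-only tables it feeds, and names no imputation set (cheap improvement).

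*SAP*

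**What the plan says.** SAP 5.5.2 sets out the imputation: "MI will be performed separately for saliva samples and nasopharyngeal samples and for each treatment via a two-step process for subjects with non-missing baseline". Step 1 ("mcmc impute=monotone") fills interim gaps using "var log_day1 log_day3 log_day5 log_day8 log_day14". Step 2 fills the remaining gaps by regression on earlier visits; for the last visit the code is "monotone reg(log_day14 = log_day1 log_day3 log_day5 log_day8". Neither step contains a baseline characteristic. One seed pair is given per specimen type, and no analysis set is named. Each missing value is replaced by the average of its 100 draws on the log10 scale before the tables are made.

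The tables then divide the data by factors that the model does not contain:

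- **Serostatus.** SAP Section 4 limits the mFAS to treated subjects who were antibody-negative at baseline. Table 14.2.3.2.1 is "Log10-Transformed nasopharyngeal Viral Load by Visit for Subjects with Mild and Moderate Disease at Baseline, Modified Full Analysis Set", and Table 14.2.5.2 is its saliva counterpart.
- **Severity.** Tables 14.2.3.1.2, 14.2.3.2.2 and 14.2.3.3.2 cover mild disease only, for nasopharyngeal load. Saliva has no mild-only table.

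SAP 3.3 expects that the enlarged Final Cohort "will lead to approximately 90 seropositive and 90 seronegative subjects". SAP 5.5.1 already uses both factors as Cox covariates, coded ANTIBODY and DSSTATUS.

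On treatment, SAP 5.5.2 disagrees with itself. The text imputes for each treatment, the printed code has no BY treatment, and the non-convergence fallback says "only one of the 3 dummy variables for treatment will be needed in the first call to PROC MI".

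**The concern.** When completed data are tabulated by a subgroup, the imputation model should contain the variable that defines the subgroup. Otherwise a missing Day 8 or Day 14 value in a seronegative subject is predicted from a regression averaged over both serostatuses. If seropositive subjects clear virus faster than their observed loads already show, the filled-in value is too low. Because the average draw enters the table directly, the mean and geometric mean carry the same pull.

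The mFAS virology tables are there to show the course in antibody-negative subjects, so a pull toward the seropositive course blurs what they are for. The same reasoning applies to the mild-only tables if severity predicts viral load.

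Missing values will not come from dropout alone. SAP 5.5.2 also sets to missing any post-baseline sample with a specimen violation, an inconclusive N1 result or an undetermined RNase P control.

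**Working it through.** **The plan's own figure.** The documents give no number for the imputation or for viral-load means. The only power figure for the seronegative set is at least 90% for the first primary endpoint (SAP 3.3). It reproduces: events = 0.8 × (60 × 0.85 + 30 × 0.75) = 58.8; √(58.8 × 2/3 × 1/3) × |ln 0.4| − 1.96 = 3.31 − 1.96 = 1.35; power 0.91. It concerns symptom resolution and does not depend on the imputation.

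**First-order size.** Pull on the mFAS mean ≈ f × w × d, where

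- f is the share of seronegative values missing. SAP 3.3 allows up to 20% dropout; no rate of missing samples is given.
- w is the seropositive share of the imputation set. It is 90/180 = 0.50 as stated, or 75/180 = 0.42 if the first 30 subjects are all seronegative and only the 150 optional subjects split equally.
- d is the serostatus gap in log10 viral load left after conditioning on the other viral loads. It is not in the documents, so a range is assumed.

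| f | w | d = 0.25 | d = 0.5 | d = 1.0 | d = 1.5 |
|---|---|---|---|---|---|
| 20% | 0.50 | 0.025 | 0.050 | 0.100 | 0.150 |
| 20% | 0.42 | 0.021 | 0.042 | 0.083 | 0.125 |
| 10% | 0.50 | 0.013 | 0.025 | 0.050 | 0.075 |
| 5% | 0.50 | 0.006 | 0.013 | 0.025 | 0.038 |

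The residual d is smaller than the raw gap between serostatuses, because observed loads carry part of the serostatus information. Simulation shows by how much.

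**Simulation 1.** 2,000 groups of 120 (the RD-X19 arm of 180 at 2:1), half seropositive, five visits, SD 1.5, AR(1) correlation 0.6, monotone missingness from Day 8, conditional-mean imputation. All of these except the arm size and serostatus split are assumptions. Bias of the seronegative mean at Day 8 / Day 14:

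| Raw gap, Day 8 / Day 14 | 10% missing | 20% missing |
|---|---|---|
| 1.0 / 0.8 | −0.031 / −0.029 | −0.064 / −0.060 |
| 1.5 / 1.2 | −0.042 / −0.040 | −0.080 / −0.072 |
| 2.0 / 1.5 | −0.046 / −0.041 | −0.097 / −0.081 |

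With serostatus in the model the bias was 0.00 throughout.

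**Simulation 2.** Multivariate-normal imputation with posterior draws averaged, one arm of 120, half seropositive, dropout reaching about 20% by Day 14 (about 15% by Day 8), 25 replicates. With an assumed extra decline of 0.5 to 1.0 log10 in seropositives, the viral-load-only model put mFAS means 0.026 to 0.058 too low at Day 8 and 0.019 to 0.049 too low at Day 14 (Monte Carlo SE 0.012 to 0.018). Against the model with serostatus on the same data, the shift was −0.02 to −0.06. With no extra decline, the two models agreed within 0.01.

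**Scale.** 10^−0.02 = 0.95 and 10^−0.097 = 0.80, so geometric means would be about 5% to 20% low. With SD 1.5 and 60 seronegative RD-X19 subjects, the standard error of a mean is 1.5/√60 = 0.19 log10, so 0.10 is about half a standard error.

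**The case against.** The strongest reply is that the pull depends on three conditions that the documents do not establish: one run over both serostatuses, a serostatus gap beyond what the observed loads explain, and missing values in seronegatives. That stands. If the imputation were run within the mFAS, its means would not be pulled at all. FAS means could still shift where missingness differs by serostatus, by about 0.02 to 0.03 log10 for 10% in one group and 20% in the other under the first simulation's assumptions.

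It also stands that the effect is small against sampling error, that log10 means are displayed to one decimal, and that 20% is a planning ceiling.

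A reader might infer more than the documents support:

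- **That the RD-X19 versus sham comparison is biased.** The tables give no contrast and no p-value, and with imputation by arm a similar pull largely cancels. It need not cancel fully: the RD-X19 Final Cohort column stands beside Pooled Sham, which includes Cohort A, and Protocol 6.3 aims Cohort A at seronegatives. But no contrast bias was computed.
- **That the mild-only tables are biased.** The omission is the same, but no size was computed and the documents give no severity gap in viral load.
- **That values are filled from past loads only.** This is true of step 2, but step 1 also uses later visits.

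The objection that extra terms strain small arms is fair. Cohort A sham targets 10 seronegative subjects, and a Day 14 regression with an intercept, four viral loads and two covariates has seven coefficients.

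**Conclusion.** The imputation model omits the variables that define subsets it serves, and its analysis set is not stated; both follow directly from SAP 5.5.2 and the table list. Whether mFAS means are in fact pulled is conditional. Under the natural reading of a single run, and with a residual serostatus gap, they move toward the seropositive course, mainly in the Final Cohort and pooled columns.

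The size is about 0.02 to 0.10 log10 at 20% missing, about half that at 10%, and near zero without a residual gap. It rests on the assumed gaps, SDs and correlations above. Only descriptive secondary and exploratory tables are concerned; no test or primary conclusion changes. This is a cheap improvement, not a flaw that threatens the trial.

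**What to change.** In SAP 5.5.2, for both specimens:

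1. Add ANTIBODY and DSSTATUS to the step 1 VAR list and to every step 2 MONOTONE REG statement, at least for the Final Cohort arms. List them ahead of the Day 1 load in both VAR statements so that the pattern stays monotone. Drop a term where a Cohort A arm has one serostatus or is too small, and say so.
2. State that a single FAS imputation feeds the FAS, mFAS, PP and mild-only tables.
3. Reconcile how treatment enters. SAP 5.5.1 codes four treatment groups, so three dummies would fit one joint model with treatment as a covariate, whereas the text describes separate fits. Run as printed, the code would do neither and would mix the arms. Choose one and make text, code and fallback agree.

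The cost is two baseline variables already collected and coded, and no new data. The downside is one or two more parameters per regression, which small Cohort A arms may not support; dropping terms there leaves arms with different imputation models, which should be disclosed in the table footnotes.
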